8. STATISTICAL METHODOLOGY

8.1. General

Listings will be provided for all data captured in the database. Listings will include all subjects assigned to the all subjects population and include data up to the point of study completion or discontinuation. Subjects are generally considered to have completed the study if they completed all protocol-specified procedures and assessments for the end-of-treatment visit. Any subject who discontinued the study will be identified accordingly in the listings. Summaries and statistical analyses will include the subjects assigned to the relevant population based on data type.

Data analysis will be performed using the SAS[®] statistical software package Version 9.4 (or higher if upversioned during the study).

Analysis Data Model (ADaM) datasets will be prepared using Clinical Data Interchange Standards Consortium (CDISC) ADaM Version 2.1 (or higher if upversioned during the study) and CDISC ADaM Implementation Guide Version 1.1 (or higher if upversioned during the study). Pinnacle 21 Community Validator Version 2.2.0 (or higher if upversioned during the study) will be utilized to ensure compliance with CDISC standards.

Caution should be used when interpreting results from the statistical analyses conducted in this study because the sample size is not based on power calculations.

Where reference is made to ‘all calculations’, this includes, but is not limited to, summary statistics, statistical analyses, baseline derivation, changes from baseline, percentage changes from baseline, and any parameter derivations.

8.1.1. Calculation of the Summary Statistics

For continuous data the following rules will be applied:

- Missing values will not be imputed, unless specifically stated otherwise.
- Unrounded data will be used in the calculation of summary statistics.

- If the number of subjects with valid observations (n) < 3 , summary statistics will not be calculated, with the exception of n , minimum, and maximum.
- As Early Termination data is not associated with any scheduled timepoint, it will be excluded from all calculations of summary statistics.

For categorical data the following rules will be applied:

- If the categories of a parameter are ordered (eg, AE severity), all categories between the possible minimum and maximum categories will be included, even if $n = 0$ for a given category. If the categories are not ordered (eg, race), only those categories for which there is at least 1 subject represented will be included.
- Missing values will not be imputed, with the exception of AEs where the ‘worst-case’ approach will be taken (see [Section 8.6.1](#)), or unless specifically stated otherwise. A ‘missing’ category will be included for any parameter for which information is missing. This will ensure that the population size totals are consistent across different parameters.

All protocol deviations and data issues (eg, missing data or data outside of the protocol windows) that occur during the study, including those related to COVID-19, will be considered prior to database lock for their severity/impact on how the data will be displayed and analysed statistically.

8.1.2. Repeat and Unscheduled Readings

For vital signs and ECG data only, any predose value recorded in addition to the original value or a postdose value recorded within 15 minutes of the original value will be defined as a repeat value; any postdose value recorded more than 15 minutes after the original value will be defined as an unscheduled value. For all other data types (eg, laboratory parameters), any value recorded in addition to the original value will be defined as an unscheduled value.

The original value will be replaced by the last associated repeat value in all calculations, with the exception of the ECG outlier analysis (see [Section 8.6.4](#)).

As unscheduled values are not associated with any scheduled timepoint, they will be excluded from all calculations, with the exception of the baseline derivation (see [Section 8.1.3](#)) and ECG outlier analysis (see [Section 8.6.4](#)).

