8.6.2. Clinical Laboratory Parameters

All clinical laboratory parameters, with changes from baseline, will be listed; any value outside the clinical reference range will be flagged.

Separate listings will be provided for any parameter for which there is any individual subject value outside the respective clinical reference range.

Summary tables and boxplots by treatment and timepoint will be provided for chemistry, and hematology parameters, with changes from baseline.

Shifts from baseline tables will be provided for chemistry and hematology parameters.

Values recorded as <x, ≤x, >x, or ≥x will be displayed in the listings as recorded. For the derivation of listing flags, calculation of summary statistics, and presentation in the figures, <x and ≤x values will be set to half of x, whereas >x and ≥x values will be set to x.

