8.6.3. Vital Signs Parameters

All vital signs parameters, with changes from baseline, will be listed; any value outside the clinical reference range will be flagged.

Summary tables and boxplots by treatment and timepoint will be provided for all vital signs parameters, with changes from baseline.

8.6.4. 12-lead Electrocardiogram Parameters

All 12-lead ECG parameters, with changes from baseline, will be listed; any value outside the clinical reference range will be flagged.

Summary tables and boxplots by treatment and timepoint will be provided for all 12-lead ECG parameters, with changes from baseline.

An outlier analysis will be performed for QT interval corrected for heart rate using Fridericia's formula (QTcF). The analysis will include all individual original, repeat, and unscheduled postdose values.

The maximum postdose values will be summarized by treatment according to the following categories:

- ≤ 450 ms
- >450 and ≤ 480 ms (all instances flagged in the listing)
- >480 and ≤ 500 ms (all instances flagged in the listing)
- >500 ms (all instances flagged in the listing)

The maximum increases from baseline will be summarized by treatment according to the following categories:

- ≤ 30 ms
- >30 and ≤ 60 ms (all instances flagged in the listing)
- >60 ms (all instances flagged in the listing)

An extra listing presenting subjects with a QTcF >500 ms and/or an increase from baseline of >60 ms will be produced only if at least one occurrence of either of these criterion occur.

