10. SIGNIFICANT CHANGES FROM THE PROTOCOL-SPECIFIED ANALYSES

EIDD-2801 concentration data were not quantifiable in some treatment groups and therefore PK parameters were not calculable. These affected groups will not have any parameter data presented and any analysis based upon these parameters will not be performed. Where limited samples were quantifiable (i.e. not a minimum of 3 consecutive concentrations with at least one after C_{max}) C_{max} and t_{max} may be reported.

The protocol indicated that the DMID toxicity grading scale would be used to grade laboratory parameters after taking into consideration institutional normal parameter ranges. The decision was made to evaluate out of reference laboratory parameters in the CSR only rather than using the DMID grading, as for several parameters the reference ranges used at the site were not consistent with the toxicity grading table provided in the protocol. Therefore, treatment-emergent toxicities based on DMID grading will not be reported and shift tables will be reported instead.

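### Laboratory shift tables, which replace DMID grading, exclude unscheduled postdose values and can miss a subject's only or worst abnormal result

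*SAP*

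**What the plan says.** Section 8.1.2 separates repeat readings from unscheduled ones, but the repeat category exists only for vital signs and ECGs. For all other data types, laboratory parameters included, "any value recorded in addition to the original value will be defined as an unscheduled value". The rule for such values is: "As unscheduled values are not associated with any scheduled timepoint, they will be excluded from all calculations". The sentence goes on "with the exception of the baseline derivation" and names the ECG outlier analysis as the second exception. It names no laboratory output.

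Section 8.1 leaves the scope of the term open: "this includes, but is not limited to, summary statistics, statistical analyses, baseline derivation, changes from baseline". Shift tables are neither listed nor exempted.

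Section 8.6.2 gives the shift tables one sentence: "Shifts from baseline tables will be provided for chemistry and hematology parameters". It does not say whether they are built at each timepoint or on the worst value, or which categories they use. Section 10 explains their role: "treatment-emergent toxicities based on DMID grading will not be reported and shift tables will be reported instead".

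Early-termination data have a separate rule in Section 8.1.1, placed among the bullets for continuous data: "As Early Termination data is not associated with any scheduled timepoint, it will be excluded from all calculations of summary statistics".

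For QTcF, Section 8.6.4 summarises each subject's maximum postdose value and maximum increase, and says: "The analysis will include all individual original, repeat, and unscheduled postdose values".

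**The concern.** The stated reason for excluding unscheduled values is that they belong to no scheduled timepoint. That is sound for means and boxplots by timepoint. It does not carry over to a table that asks whether a subject's laboratory value ever left its baseline category, because such a table needs no timepoint. The SAP accepts this for QTcF and does not extend it to laboratory data.

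The gap matters because of what the shift tables replace. With DMID grading of laboratory values dropped, they are the only planned tabulation of laboratory abnormality apart from AEs. The other laboratory summaries in 8.6.2 are by-timepoint tables and boxplots, which fall under the same exclusion. Safety laboratory assessments are one of the five named components of the primary endpoints for Parts 1 and 3 (Section 3.1). A subject who was abnormal only at an unscheduled draw would appear in the tables as having no shift.

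**Working it through.** The SAP states no figure on this point. Section 5 reports no formal sample size calculation, and Section 8.6.6 plans no inferential safety analysis. The check is therefore mainly one of text, followed by a simple illustration of size.

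**Does the exclusion reach the shift tables?**

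1. A postdose laboratory value taken in addition to the scheduled one is unscheduled (8.1.2).
2. Unscheduled values are left out of all calculations, a term whose list is open-ended (8.1).
3. Neither exception helps. The baseline exception admits predose values only, and the other concerns ECGs.
4. No other section exempts the shift tables.

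As written, an unscheduled postdose laboratory value cannot enter them. There is also an asymmetry: an unscheduled predose value can set the baseline, but an unscheduled postdose value cannot show a shift from it.

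**Does the early-termination rule reach them?** That rule covers summary statistics and stands under continuous data. The bullets for categorical data contain no counterpart, and shift tables are categorical. The text does not settle the question.

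**Which subjects are affected?** Assume that the shift categories are below, within and above the reference range; the SAP does not state this.

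| Scheduled postdose values | Unscheduled value | Effect on the shift table |
|---|---|---|
| Abnormal in one direction | Abnormal in the same direction | None; the scheduled value already counts |
| All normal | Abnormal | Subject missed |
| Abnormal in one direction | Abnormal in the other direction | Second shift missed |

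With finer categories, a more extreme retest could also be lost.

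**Size of one missed subject.** Section 5 gives 6 active subjects per SAD or MAD cohort and 10 in the food-effect cohort.

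- SAD or MAD cohort: 1/6 = 16.7%, reported as 0/6 = 0%, a change of 16.7 percentage points.
- Food-effect cohort: 1/10 = 10%, reported as 0/10, a change of 10 points.

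**Chance of at least one miss in a cohort.** Let p be the probability that a subject's only abnormal post-baseline value is an excluded one. The SAP gives no such figure, so p is assumed over a range. For 6 independent subjects the chance is 1 − (1 − p)^6:

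| Assumed p | Chance of at least one missed among 6 |
|---|---|
| 2% | 1 − 0.98^6 = 11.4% |
| 5% | 1 − 0.95^6 = 26.5% |
| 10% | 1 − 0.90^6 = 46.9% |
| 20% | 1 − 0.80^6 = 73.8% |

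These values show sensitivity to an unknown rate. They do not estimate what happened in the trial.

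**The case against.** The strongest reply is that nothing is hidden. Section 8.1 lists all captured data. Section 8.6.2 flags every out-of-range laboratory value and adds separate listings for any parameter with such a value. Section 10 says out-of-reference laboratory results will be evaluated in the CSR. AEs remain DMID-graded and tabulated by severity and treatment. With 6 active and 2 placebo subjects per cohort, reading listings is practical, and Section 9 rests escalation on review of blinded safety and tolerability data, with no mention of shift tables. All of this stands. It limits the consequence, but a listing gives no count to set beside another dose.

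A second reply is that by-timepoint shift tables are a legitimate design in which values without a timepoint have no place, and that the TFL shells, which are not at hand, may settle the layout. This is fair, but the rule in 8.1.2 would still bind, and a by-timepoint layout cannot show a subject's worst value between visits.

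A reader might infer more than the text supports:

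- *That the most informative values are systematically removed.* Laboratory retests never replace the original, so the abnormal scheduled value that prompted a retest stays in the table. The loss needs a subject who is normal at the scheduled draws, for example one with a symptom-driven draw.
- *That early-termination values are certainly barred.* The rule in 8.1.1 is narrower than that.
- *That the tables are biased most at higher doses.* The SAP gives no rate or dose pattern of extra draws.
- *That the primary safety endpoint as a whole is understated.* Physical examinations, vital signs, ECGs and AEs do not depend on the laboratory shift tables.
- *That interval limits show a large effect.* Setting a two-sided 95% interval for 1/6 (0.4% to 64%) against a one-sided 95% upper limit for 0/6 (39%) mixes conventions. The matching two-sided upper limit is 1 − 0.025^(1/6) = 46%. No such limits are planned.

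**Conclusion.** The point holds in a limited form. Following the SAP as written, a subject whose only or worst abnormal postdose laboratory value came from an unscheduled draw can be missing from the chemistry and hematology shift tables that stand in for DMID grading. Whether the same applies to early-termination values is undetermined. Each such subject costs one count, 16.7 percentage points in a 6-subject active cohort, if no scheduled value already places the subject in the same category. How often this occurs cannot be judged from the SAP.

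The effect stops at the laboratory tables, since the values remain visible in listings, the CSR evaluation and any related AEs. This is a worthwhile, inexpensive improvement and not a defect that must be cured before the analysis can be trusted. The reason to act is consistency: for QTcF the SAP already uses the method that avoids the problem.

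**What to change.** - **Section 8.1.2:** add the laboratory shift tables to the exceptions, and limit the exclusion of unscheduled values to by-timepoint summaries.
- **Section 8.6.2:** define the chemistry and hematology shift tables as baseline to worst post-baseline value, with the lowest and the highest value taken separately, over all scheduled, unscheduled and early-termination records. State the categories used. This mirrors the QTcF maximum in 8.6.4.
- **Section 8.1.1:** limit the early-termination exclusion to by-timepoint summaries, so that its reach is no longer in doubt.

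By-timepoint means and boxplots stay on scheduled values. No new data are needed, because all captured values are already listed. The cost is a SAP wording change, a small programming change with matching table shells, and tables that may look slightly less favourable. Section 1 requires the SAP to be final before the clinical database is locked, so the change belongs in the text before then.

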8.1.3. Definitions of Baseline, and Change from Baseline

The baseline will be defined as the last value recorded prior to dosing (Part 1)/dosing in each period (Part 2)/the first dose (Part 3). If the date/time of the value is incomplete or missing, it will be excluded from the baseline calculation, unless the incomplete date/time indicates the value was recorded prior to dosing (Part 1)/dosing in each period (Part 2)/the first dose (Part 3).

Individual changes from baseline will be calculated by subtracting the individual subject’s baseline value from the value at the timepoint. The mean change from baseline will be defined as the mean of the individual changes from baseline for all subjects.

See [Section 8.1.2](#) for more detail on handling repeat and unscheduled readings in the calculations.

8.2. Subject Disposition and Population Assignment

Subject disposition and population assignment will be listed.

A summary table by treatment (Part 1 and Part 3)/treatment sequence (Part 2) will be provided, based on the all subjects population.

8.3. Screening Demographics

The screening demographics including age, sex, race, ethnicity, height, body weight, and body mass index will be listed.

A summary table by treatment (Part 1 and Part 3)/treatment sequence (Part 2) will be provided, based on the safety population.

8.4. Prior and Concomitant Medication

Prior medication will be defined as medication that ends prior to dosing (Part 1)/the first dose (Part 2 and Part 3). Concomitant medication will be defined as medication that starts during or after dosing (Part 1)/the first dose (Part 2 and Part 3) or starts but does not end prior to dosing (Part 1)/the first dose (Part 2 and Part 3).

Prior and concomitant medications will be coded using the World Health Organization Drug Dictionary (WHODrug) Global, Format B3, Version March 2020 (or later if upversioned during the study). Prior and concomitant medications will be listed.

8.5. Pharmacokinetic Assessments

8.5.1. Pharmacokinetic Analysis

PK parameters will be determined using non-compartmental methods in validated software program, Phoenix WinNonlin (Certara, Version 8.1 or higher).

The following parameters will be calculated where possible from the plasma concentrations of EIDD-2801 and EIDD-1931:

Parameter	Units ^a	Definition
AUC _{last}	h*ng/mL	the area under the plasma concentration-time curve, from time 0 to the last measurable non-zero concentration ^b , (Part 1, Part 2 and Part 3).
AUC _{0-inf}	h*ng/mL	the area under the plasma concentration-time curve from time 0 extrapolated to infinity ^{b,c} . (Part 1, Part 2, and Day 1 dose of Part 3).
AUC _τ	h*ng/mL	area under the plasma concentration-time curve during a dosing interval ^b (Part 3 only)
%AUC _{extrap}	%	percentage of AUC _{0-inf} that is due to extrapolation from the last quantifiable concentration to infinity

$\%AUC_{\tau, \text{extrap}}$	%	percentage of AUC_{τ} that is due to extrapolation from the last quantifiable concentration to the end of the dosing interval
C_{max}	ng/mL	maximum observed concentration
t_{max}	h	time of the maximum observed concentration
t_{last}	h	time of the last quantifiable concentration
λ_z	1/h	apparent terminal elimination rate constant
$t_{1/2}$	h	apparent terminal elimination half-life
CL/F	L/h	apparent clearance following an extravascular dose (EIDD-2801 only)
V_z/F	L	apparent volume of distribution during the terminal phase following and extravascular dose (EIDD-2801 only)
C_{trough}	ng/mL	plasma concentration at the end of the dosing interval (Part 3 only)
MR_{AUC}		EIDD-1931:EIDD-2801 ratio based on $AUC_{0-\text{inf}}$ (Day 1) or AUC_{τ} (Part 3 only, Day 6)
$MR_{C_{\text{max}}}$		EIDD-1931:EIDD-2801 ratio based on C_{max}
$RA_{AUC_{\tau}}$		observed accumulation ratio based on AUC_{τ} (Part 3 only).
$RA_{C_{\text{max}}}$		observed accumulation ratio based on C_{max} (Part 3 only).

^a Units are based on concentration units (provided by bioanalytical lab) and dose units used in the study.

^b AUC will be calculated using the linear trapezoidal rule for increasing concentrations and the logarithmic rule for decreasing concentrations (linear up/log down rule).

^c Based on last observed quantifiable concentration

In addition, dose normalized parameters will be calculated for AUC_{last} , $AUC_{0-\text{inf}}$, AUC_{τ} and C_{max} , calculated by dividing the parameter by the administered dose in mg. These parameters will follow the same naming convention as the original parameter with the prefix 'D', eg, DC_{max} .

The following parameters will be where possible from the urine concentrations of EIDD-2801 and EIDD-1931:

Parameter	Units ^a	Definition
Ae_{t1-t2}	mg	amount of the dose administered recovered in urine over the time interval t1 to t2 (calculated by interval and cumulatively)
Fe_{t1-t2}	%	percentage of the dose administered recovered in urine over the time interval t1 to t2 (calculated by interval and cumulatively)
CL_R	L/h	renal clearance

^a Units are based on concentration units (provided by bioanalytical lab) and dose units used in the study.

Additional PK parameters may be determined where appropriate.

Pharmacokinetic analysis will, where possible, be carried out using actual blood sampling times postdose. If an actual time is missing, the sample concentration result will be treated as missing unless there is scientific justification to include the result using the nominal time.

Pharmacokinetic parameters will be derived where possible for all subjects. Data from subjects with incomplete profiles (missed blood draws, lost samples, samples unable to be quantified) may be used if PK parameters can be estimated using the remaining data points.

The following molecular weights (MW) will be used in calculations where required

EIDD-2801 329.31 g/mol

EIDD-1931 259.22 g/mol

C_{max} , t_{last} and t_{max} will be obtained directly from the concentration-time profiles. If C_{max} occurs at more than 1 timepoint, t_{max} will be assigned to the first occurrence of C_{max} .

Parent : prodrug ratios will be calculated as follows:

$$MR_{AUC} = (AUC_{0-inf, EIDD-1931}/MW_{EIDD-1931}) / (AUC_{0-inf, EIDD-2801}/MW_{EIDD-2801})$$

$$MR_{C_{max}} = (C_{max, EIDD-1931}/MW_{EIDD-1931}) / (C_{max, EIDD-2801}/MW_{EIDD-2801})$$

AUC_{last} or other common partial area may be used to determine MR_{AUC} if AUC_{0-inf} cannot be reliably calculated for the majority of subjects.

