8.5.1.2. Criteria for Calculation and Reporting of Area Under the Concentration-time Curve

The minimum requirement for the calculation of AUC will be the inclusion of at least 3 consecutive concentrations above the lower limit of quantification. If there are only 3 consecutive concentrations, at least 1 should follow C_{max} .

If the extrapolated area is >20%, AUC_{0-inf} (and derived parameters) may be excluded from summary statistics and statistical analysis at the discretion of the sponsor or PK analyst.

If AUC_{0-inf} cannot be determined reliably for all subjects and/or dose levels/treatments, an alternative AUC measure, such as AUC to a fixed timepoint or AUC_{last} , may be used in the statistical analysis.

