8.5.1.3. Calculation of Urinary Parameters

The amount of drug excreted in urine (A_e) and urine collection interval (t_1-t_2) will be calculated as the product of urine analyte concentration and urine volume. Where only urine sample weight is supplied, a specific gravity of 1 g/mL will be assumed, and it will be considered equivalent to urine volume. A total cumulative $A_{e0-x h}$ will be calculated by summing the $A_{e_{t_1-t_2}}$ values over the 0-x h interval, where x = end of the last collection time interval.

The percentage of the dose administered over the time interval t_1 to t_2 ($Fe_{t_1-t_2}$) as EIDD-2801 will be calculated for each urine collection interval as:

$$Fe_{t_1-t_2} = (A_{e_{t_1-t_2}} / \text{Dose}) \times 100\%.$$

The $Fe_{t_1-t_2}$ excreted as EIDD-1931 will be calculated for each urine collection interval as:

$$Fe_{t_1-t_2} = A_{e_{t_1-t_2, EIDD-1931}} / (\text{Dose}_{EIDD-2801} \times [MW_{EIDD-1931} / MW_{EIDD-2801}]) \times 100\%$$

Cumulative $Fe_{0-x h}$ will be calculated by summing the $Fe_{t_1-t_2}$ values over the 0-x h period in the same manner as $A_{e0-x h}$.

Renal clearance will be calculated as follows:

$$CL_R = A_e / AUC$$

where both A_e and AUC are determined over co-incident time ranges after dosing.

8.5.1.4. Criteria for Handling Below the Limit of Quantification or Missing Concentrations for Pharmacokinetic Analysis

Plasma concentration values that are below the limit of quantification (BLQ) will be set to a value of zero, with the following defined exceptions which will be set to missing:

- Any embedded BLQ value (between 2 quantifiable concentrations).
- BLQ values following the last quantifiable concentration in a profile.

- If an entire concentration-time profile is BLQ, it will be excluded from PK analysis.

Where 2 or more consecutive concentrations are BLQ at the end of a profile, the profile will be deemed to have terminated and any further quantifiable concentrations will be set to missing for the calculation of the PK parameters unless they are considered to be a true characteristic of the profile of the drug.

If a predose plasma concentration is missing, it may be set to zero by default.

Urine concentrations that are BLQ will be set to zero for the calculation of $Ae_{t_1-t_2}$.

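### The Day 1 MR_AUC fallback treats AUC_last as a common window, which it is not, so the ratio can be biased; the >20% extrapolation exclusion also needs a fixed rule

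*SAP*

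**What the plan says.** - **Ratio fallback (SAP 8.5.1).** MR_AUC is built on AUC_0-inf on Day 1 and on AUC_tau on Day 6. If AUC_0-inf "cannot be reliably calculated for the majority of subjects", AUC_last "or other common partial area may be used to determine" MR_AUC. The wording counts AUC_last among the common areas.
- **What AUC_last is (SAP 8.5.1 and 8.5.1.4).** It runs "from time 0 to the last measurable non-zero concentration". Section 8.5.1.4 sets to missing any "BLQ values following the last quantifiable concentration in a profile".
- **Fallback for the models (SAP 8.5.1.2).** If AUC_0-inf is not reliable, "an alternative AUC measure, such as AUC to a fixed timepoint or" AUC_last may be used. No order of preference is given.
- **Exclusions (SAP 8.5.1.2).** Above 20% extrapolation, AUC_0-inf and parameters derived from it "may be excluded from summary statistics and statistical analysis at the discretion of the sponsor or PK analyst".
- **What is already known (SAP 10).** "EIDD-2801 concentration data were not quantifiable in some treatment groups". Those groups get no parameter data and no analysis that depends on them.
- **Where the areas are used.** Section 3.1 lists AUC_0-inf and AUC_last among the Part 2 primary endpoints, and Section 4.1.2 makes Part 2 open-label. Sections 8.5.3.1 (Part 1 and Day 1) and 8.5.3.2 analyse AUC_last alongside AUC_0-inf and C_max whether or not AUC_0-inf fails.

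**The concern.** A metabolite-to-prodrug ratio is interpretable only if numerator and denominator cover the same time or are both essentially complete. AUC_last guarantees neither. The fallback is used when terminal slopes cannot be fitted or tails are large, which is when truncation matters most. The plan applies the principle elsewhere: for renal clearance, Section 8.5.1.3 requires the urine amount and the plasma area to cover matching times. It sets no such rule for MR_AUC.

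Two related gaps sit in Section 8.5.1.2. The replacement area is left open between a fixed-time AUC and AUC_last. The removal of values above 20% extrapolation is left to judgement, with no criterion for when to remove and when to keep. That judgement bears on a primary endpoint of Part 2.

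**Working it through.** The SAP gives no figure for this bias, so there is none to reproduce. It also gives no quantification limit (LLOQ), C_max, half-life, CV or sampling times. Those below are assumptions.

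**1. The ratio.** Let f be the share of AUC_0-inf that lies after an analyte's last quantifiable sample. Then, exactly:

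MR from AUC_last ÷ MR from AUC_0-inf = (1 − f1931) ÷ (1 − f2801)

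- f1931 = 1%, f2801 = 10%: 0.99 ÷ 0.90 = 1.10
- f1931 = 1%, f2801 = 30%: 0.99 ÷ 0.70 = 1.41
- both 20%: 0.80 ÷ 0.80 = 1.00
- f1931 = 20%, f2801 = 10%: 0.80 ÷ 0.90 = 0.89

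The direction therefore depends on which analyte loses the larger share.

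**2. A plausible size for f2801.** Take oral one-compartment profiles, C(t) proportional to exp(−ke·t) − exp(−ka·t), with ka 1.5 to 3 per hour and ke 0.7 to 1.0 per hour. Let t be the time when C has fallen to C_max/k, where k = C_max/LLOQ. Then

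f = [exp(−ke·t)/ke − exp(−ka·t)/ka] ÷ (1/ke − 1/ka)

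EIDD-1931 is given the same shape with k = 200, so f1931 is below 0.5%.

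| EIDD-2801 C_max/LLOQ | f2801 | Ratio relative to truth |
|---|---|---|
| 10 | 5–6% | 1.05–1.07 |
| 5 | 10–13% | 1.10–1.14 |
| 3 | 17–21% | 1.20–1.27 |
| 2 | 26–32% | 1.35–1.47 |

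This assumes sampling dense enough to follow the curve down to the LLOQ. With a discrete schedule the last quantifiable sample falls earlier. In one illustrative set, 50 mg profiles with C_max at 10, 5, 3 and 2 times LLOQ had EIDD-2801 coverage of 0.902, 0.822, 0.661 and 0.529 and ratios of 1.09, 1.20, 1.49 and 1.86. For the last, 0.982 ÷ 0.529 = 1.86.

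**3. What a common window does.** Cutting both analytes at EIDD-2801's last quantifiable time in those four profiles gave 0.949, 0.913, 0.854 and 0.809 of the true ratio, because EIDD-1931 is then truncated too. Matching the windows removes the mismatch, but a short window carries its own bias.

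**4. The AUC_last slope for EIDD-2801.** Suppose AUC_0-inf is truly proportional to dose and f falls as 1/dose. Regress ln(1 − f) on ln(dose) over 50, 100, 200, 400, 600 and 800 mg (SAP Table 1).

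| f at 50 mg | Upward shift in slope | Shift without the 50 mg group |
|---|---|---|
| 10% | 0.033 | 0.021 |
| 20% | 0.070 | 0.044 |
| 33% | 0.127 | 0.076 |

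The last column matters because a group with no quantifiable EIDD-2801 drops out. For a well-quantified EIDD-1931 the slope stayed at 1.000–1.003 in the illustrative profiles.

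**5. Consequence under the plan's rule.** Section 8.5.3.1 concludes proportionality if linearity is acceptable and the 90% CI for the slope contains 1. With 6 active subjects at each of 6 doses, the sum of squares of ln(dose) is 34.86. At an assumed CV of 30%, SD = √ln(1.09) = 0.294, and the half-width is 1.691 × 0.294 ÷ √34.86 = 0.084. The chance of excluding 1 is 10% with no shift, about 20% with a shift of 0.04 and about 55% with 0.09. Section 8.5.3.1 fits the models by formulation, so the real dose range may be narrower than the one used here.

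**The case against.** The other side has a good case on several counts.

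- **Optional fallback.** Both fallbacks are permissive, and the SAP already allows a common or fixed-time area. This stands, but nothing steers the analyst to it, and Section 8.5.1 presents AUC_last as equivalent.
- **Low stakes for the ratio.** MR_AUC is not a listed endpoint and enters no model. It is listed and summarised. This stands and limits the severity.
- **Section 10.** It says that some groups were not quantifiable, and those groups yield no ratio at all. The bias concerns only neighbouring, partly quantifiable groups. Section 8.5.1.2 also requires three consecutive quantifiable concentrations before any AUC is calculated.
- **Slope.** AUC_last is a planned parameter in its own right, so removing it as a fallback would leave its slope in the report. This stands, and the remedy has to be about how that slope is read.
- **Exclusions can be traced.** All parameters are listed, including the extrapolated percentage, and AUC_last and C_max remain for the food effect. This reduces the risk from discretion but does not supply a rule.

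A reader might infer that the ratio and the slope are inflated in every case. The documents do not support that: the direction depends on the two missed shares, and the SAP gives nothing that fixes them. A reader might also set the slope shift against an acceptance half-width of 0.08, which is ln(1.25) ÷ ln(16) for a 16-fold range. The SAP has no such margin; its criterion is whether the 90% CI contains 1.

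**Conclusion.** The point holds in limited form. Section 8.5.1 describes AUC_last as a common area, which its own definition and the handling of late unquantifiable values contradict. A Day 1 MR_AUC from the fallback can therefore compare different time windows. If EIDD-2801 is lost first, the upward bias is about 1.05- to 1.5-fold for a C_max of 10 down to 2 times LLOQ. That range rests on assumed oral one-compartment profiles followed down to the LLOQ, and coarser sampling could raise it. The bias is nil or reversed under other patterns of loss. Day 6 is not affected in this way.

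For EIDD-2801, truncation at low doses can also push the planned AUC_last slope above 1. The effect on a well-quantified EIDD-1931 is negligible.

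The discretionary 20% exclusion is a separate, document-based weakness. It leaves the set of AUC_0-inf values in a Part 2 primary analysis open to choice after results are known. Nothing in the SAP shows that the choice was, or would be, driven by results. All three items should be corrected; none invalidates the study.

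**What to change.** 1. **Section 8.5.1.** Replace AUC_last as the MR_AUC fallback with a partial AUC over one interval, the same for both analytes within a subject. Report t_last and the share of exposure covered, by analyte and dose. State what happens when EIDD-2801 becomes unquantifiable before the interval ends, since Section 8.5.1.4 sets those values to missing.
2. **Section 8.5.1.2.** If AUC_0-inf fails, prefer AUC to a pre-specified nominal time over AUC_last. Take that time from the sampling schedule, not from the latest time at which every subject happens to be quantifiable. The latter depends on the data and is set by the sparsest profile.
3. **Section 8.5.3.1.** Keep the planned AUC_last slope, but present it for EIDD-2801 next to t_last by dose and say that truncation at low doses can raise it above 1.
4. **Section 8.5.1.2, exclusions.** Make the rule fixed: AUC_0-inf with more than 20% extrapolated is excluded from the main analysis, and the result with all values is shown beside it.

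The cost is SAP wording, one partial AUC per analyte and one extra analysis. The main downside is a short window where EIDD-2801 is sparse, which can pull the ratio below its true value; the reported coverage lets the reader judge this.
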